4.4 Safety: Adverse events

The objective of analysis presented below is to evaluate the safety of study drugs through adverse events reported during the study.

Criteria	AE number Description SOC term MedDRA) PT term MedDRA) Start date and time Time since last study drug administration End date and time AE Duration Severity (mild/moderate/severe) Serious (yes/no) Expected (yes/no) Congenital anomaly or birth defect (yes/no) Significant disability (yes/no) Death (yes/no) Life threatening (yes/no) Other medically important event (yes/no) Hospitalization (yes/no) and if yes, date of hospitalization Relationship to study treatment (none / unlikely /possible / probable / highly probable / not assessable) Outcome (recovered-resolved / recovering-resolving / recovered-resolved with sequelae / not recovered-not resolved / fatal /unknown) Action taken with study product (dose increased / dose not changed / dose reduced / dose interrupted / drug withdrawn / not applicable / unknown) Other actions (yes/no) and if yes specify Concomitant medication recorded (yes/no)
Information	AEs will be coded according to the Medical Dictionary for Regulatory Activity (MedDRA). They will be classified into pre-defined standard categories according to chronological criteria: 
 - Treatment emergent AEs (TEAE): AEs that occurs for the first time or if present before worsened during an exposure to drug(s). - Non-treatment emergent AEs (NTEAE): AEs that occurs before the study drug administration. An AE occurring during the run-out will be related to the last day of treatment administration received. AEs will be individually listed per dose group, subject number, presenting: assigned dose group, verbatim, Primary System Organ Class (SOC), Lowest Level Term (LLT), Preferred Term (PT), emergence (yes or no) date and time of onset, date and time of last study drug administration before AE, duration, time from onset since last study drug administration, intensity and seriousness, relationship to

	
study drug, the required action taken and outcome.
 
The non-treatment emergent AEs will be summarised by SOC and PT for the safety set.
 
The treatment emergent AEs will be summarised by SOC, PT and dose group for the safety set. It will consist in the evaluation of the number of AEs and the number of subjects reporting these AEs.

Population	SS.
Statistical method	
For each part:
 
The TEAEs will be summarized by dose group and overall.
 
The analysis will include the evaluation of the number of adverse events, the number of subjects reporting these adverse events and the % of subjects within the dose group. In case of few adverse events (≤ 5), only a listing will be prepared by dose group and subject.
 
TEAEs will be individually listed per dose group, subject, emergence, day, SOC, LLT, PT, date and time of onset and offset, time since last product administration, duration, intensity and seriousness, relationship to study product, action taken and outcome.
 
NTEAEs will be summarised by dose group and subject.
 
Serious adverse events (SAEs) will be summarised by dose group and subject.

Title of tables	
For each part:
 
Treatment emergent AEs - SS - By dose group.
 
Listing of treatment emergent AEs - SS - By dose group, subject, SOC, LLT and PT.
 
NTAEs - By dose group.
 
Listing of NTAEs by dose group, subject, SOC, LLT and PT. - SS.
 
SAEs - By dose group.
 
Listing of SAEs by dose group, subject, SOC, LLT and PT - SS.

4.5 Safety: Laboratory criteria

The objective of analysis presented below is to evaluate the safety laboratory variables.

Biochemistry, hematology and hemostasis criteria

Criteria	
	Biochemistry Creatinine (μmol/L) Glucose (mmol/L) Total protein (g/L) Urea (mmol/L) Albumin (g/L) Globulin (albumin/globulin ratio) Total cholesterol (mmol/L) Triglycerides (mmol/L) Sodium (mmol/L) Potassium (mmol/L) Chloride (mmol/L) Calcium (mmol/L) Uric acid (IU/L) AST (IU/L) ALT (IU/L) GGT (IU/L) Alkaline phosphatase (IU/L) CPK (IU/L) Total bilirubin (μmol/L) Conjugated bilirubin (μmol/L) LDH (IU/L) LDL (mmol/L) HDL (mmol/L) Phosphore (mmol/L) Hematology Hemoglobin (g/L) Hematocrit (no unit) Red blood cells (Tera/L) White blood cells (Giga/L) Neutrophils (Giga/L) Eosinophils (Giga/L) Basophils (Giga/L) Lymphocytes (Giga/L) Monocytes (Giga/L) Platelets (Giga/L) Reticulocytes (Giga/L) MCV (fL) MCH (fmol) MCHC (mmol/L) Hemostasis aPTT subject (s) aPTT ratio Prothrombin time (s) Prothrombin level

Information	
Part A: criteria assessed at screening, D-1, D2 and at end of study visit (D4.).
 
Part A, baseline: last assessed value at D-1.
 
Emergent value is defined as any normal value at pre-dose assessment (baseline value) according to laboratory range becoming abnormal at post-dose assessment or lower (upper) abnormal baseline value becoming upper (lower) abnormal at post-dose assessment.
 
Laboratory ranges are reported in database.

Population	SS.
Statistical method	
For each criterion
 
Values, position according to laboratory range and clinical assessment will be described at screening, baseline, each scheduled assessment during treatment phase and at end of study visit overall.
 
Change between the values from baseline to each scheduled assessment during treatment phase and end of study visit will be described by dose group and overall.
 
Listing of emergent values according to laboratory range from Baseline to each scheduled assessment during treatment phase and end of study visit by dose group and subject.

Title of tables	
For each criterion
 
Name of criterion (unit):
 
Values, position according to laboratory range and clinical assessment at screening, baseline, during treatment phase and at end of study visit.
 
Change between the values from baseline to during treatment phase and to end of study visit.
 
Listing of emergent values from baseline to during treatment phase and to end of study visit by dose group and subject.

Urinalysis and microscopic criteria

Criteria	
Urine appearance (clear/slightly cloudy/cloudy/opaque) Urine color (pale yellow/dark yellow/brown/red)
 
For each criterion, result and clinical assessment (normal/abnormal NCS/abnormal CS)
 
Urinalysis
 
pH
 
Ketone bodies (negative/positive)
 
Protein (negative/positive)
 
Glucose (negative/positive)
 
Blood (negative/positive)
 
Leucocytes (negative/positive)
 
Nitrite (negative/positive)
 
Urobilinogen bodies (negative/positive)
 
Bilirubin bodies (negative/positive)
 
Nitrite (negative/positive)

-----------------	--

	
Specific density
 
Microscopic analysis
 
Red blood cells
 
Crystallography
 
Flat cells
 
Round cells
 
Cylinders
 
Mucus
 
Bacteria

Information	
Part A: criteria assessed at screening, D-1, D2 and at end of study visit (D4).
 
Part A: baseline: last assessed value at D-1.
 
Emergent value is defined as any normal value at pre-dose assessment (baseline value) according to laboratory range becoming abnormal at post-dose assessment or lower (upper) abnormal baseline value becoming upper (lower) abnormal at post-dose assessment.
 
Laboratory ranges are reported in database.

Population	SS.
Statistical method	
pH and specific density: same method as for biology criteria.
 
For each qualitative criterion
 
Result will be described at screening, baseline, each scheduled assessment during treatment phase and at end of study visit.
 
Listing of emergent values from baseline to each scheduled assessment during treatment phase and to end of study visit by dose group and subject.
 
Microscopic criteria
 
Listing of microscopic criteria by subject and visit.

Title of table	
pH and specific density: same tables as for biology criteria.
 
For each qualitative criterion:
 
Name of criterion:
 
Result at screening, baseline, during treatment phase and at end of study visit by dose group and overall.
 
Listing of emergent values from baseline to during treatment phase and to end of study visit by dose group and subject.
 
Microscopic criteria
 
Listing of microscopic criteria by dose group, subject and visit.

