10.1.2.2. Physical examination, ECG and vital signs (for each part)

Physical examination, ECGs (including QTcF) and vital signs recorded during the study will be individually listed and quantitative parameters will be summarised by using descriptive statistics.

For vital signs and ECG parameters, values and clinically potentially significant abnormalities will be described by treatment and overall, at screening, inclusion, baseline (D1 pre-dose), each scheduled assessment during treatment phase and at the end of the study.

For vital signs and ECG parameters, change between the value at baseline and the value during at each scheduled assessment during treatment phase and at the end of study visit will be described for each parameter by treatment and overall.

In general, appropriate descriptive statistics according to the nature of the variable will be applied: categorical variables will be presented using counts and percentage, whilst continuous variables will be presented using mean, standard deviation (SD), median, minimum, maximum, coefficient of variation (CV(%)) and number of subjects.

Appropriate inferential statistics, based on variable characteristics, will be applied, if consistent.

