10.1.2.3. Laboratory parameters (for each part)

All laboratory values recorded during the study will be individually listed and flagged for values outside reference ranges and for clinical relevance (assessed by investigator). Quantitative parameters will be summarised by descriptive statistics.

Values, position according to laboratory range and clinical assessment will be described at screening, baseline (D-1), during the treatment phase and at the end of study by treatment for studies and overall.

Change between the value at baseline and the value during treatment phase and at the end of study visit will be described for each parameter by treatment and overall.

All quantitative and qualitative urinary test results will be listed, sorted by treatment for studies in parallel groups or by sequence for crossover studies.

Serology, ABT and DOA test results will be listed for each subject.

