4.6 Safety: Vital signs

The objective of analysis presented below is to evaluate the safety of study drugs through vital signs criteria.

Blood pressure, heart rate and oral body temperature

Criteria	Supine systolic blood pressure (mmHg) Supine diastolic blood pressure (mmHg) Supine heart rate (bpm) Standing systolic blood pressure (mmHg) Standing diastolic blood pressure (mmHg) Standing heart rate (bpm) Oral temperature (°C) Result (normal/abnormal) Clinically significant (yes/no) Abnormal Finding/Relevant comments Orthostatic hypotension (yes/no)
Information	
Criteria assessed at screening, D-1, D1 (pre-dose, T1h, T3h, T5h, T8h, T12h), D2 (T24h) and at end of study visit (D4)
 
Part A: baseline: last assessed value at D1 pre-dose.
 
Emergent value is defined as any normal value at pre-dose assessment (baseline value) according to normal range becoming abnormal at post-dose assessment or lower (upper) abnormal baseline value becoming upper (lower) abnormal at post-dose assessment.
 
Normal ranges values are reported in appendix.
 
Result and clinically significant will be summarised in one 3-class criterion (normal/abnormal NCS/abnormal CS).
 
Systolic orthostatic hypotension: when (supine-standing) SBP \geq20 mmHg.
 
Diastolic orthostatic hypotension: when (supine-standing) DBP \geq20 mmHg.

Population	SS.
Statistical method	
For each criterion
 
Values, position according to normal ranges values will be described at screening, D-1, baseline, each scheduled assessment during treatment phase and at end of study visit overall.
 
Change between the values from baseline to each scheduled assessment during treatment phase and end of study visit will be described by dose group and overall.
 
Listing of emergent values according to normal ranges values from baseline to each scheduled assessment during treatment phase and end of study visit by dose group and subject.
 
Orthostatic hypotension reported will be listed by dose group,

	subject and day(time)-point.

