Title of tables	
For each criterion
 
Name of criterion (unit):
 
Values, position according to normal ranges values at screening, D-1, baseline, during treatment phase and at end of study visit and change from baseline.
 
Listing of emergent values from baseline to end of study visit by dose group and subject.
 
Vitals: Result and clinical significance at each day(time) point assessment from screening to end of study.
 
Orthostatic hypotension: Listing by dose group, subject and daytime-point.

Weight

Criteria	Weight (kg)
Information	Criteria assessed at D-1 and at end of study visit (D4) Baseline: last assessed value at D-1.
Population	SS
Statistical method	Value at baseline and at end of study visit and change from baseline by dose group and overall.
Title of tables	Weight (kg): Value at baseline and at end of study visit and change from baseline by dose group and overall.

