4.8 Safety: ECG

The objective of analysis presented below is to evaluate the safety of study drugs through ECG criteria.

Criterion	Heart rate (bpm) PR (ms) QRS (ms) QT (ms) QTc Fridericia (ms) Result (normal/abnormal) Comment Clinically significant (yes/no)
Information	
Part A: criteria assessed at screening, D-1, D1 (pre-dose, T1h, T2h, T3h, T4, T6h, T8h, T12h), D2 (T24h), D3 (T48h) and at end of study visit (D4).
 
Baseline: last assessed value at D1 pre-dose.
 
Emergent value is defined as any normal value at pre-dose assessment (baseline value) according to normal range becoming abnormal at post-dose assessment or lower (upper) abnormal baseline value becoming upper (lower) abnormal at post-dose assessment.
 
Normal ranges values are reported in appendix.
 
Result and clinically significant will be summarised in one 3-class criterion (normal/abnormal NCS/abnormal CS).

Population	SS.
Statistical method	
For each criterion
 
Values, position according to normal ranges values will be described at screening, D-1, baseline, each scheduled assessment during treatment phase and at end of study visit overall.
 
Change between the values from baseline to each scheduled assessment during treatment phase and end of study visit will be described by dose group and overall.
 
Listing of emergent values according to normal ranges values from Baseline to each scheduled assessment during treatment phase and end of study visit by dose group and subject.

Title of tables	
For each criterion
 
Name of criterion (unit):
 
Values, position according to normal ranges values at screening, D-1, baseline, during treatment phase and at end of study visit and change from baseline.
 
Listing of emergent values from baseline to end of study visit by dose group and subject.
 
ECG: Result and clinical significance at each day(time) point assessment from screening to end of study.

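### SAP 4.5, 4.6 and 4.8 summarise laboratory, vital-sign and ECG values overall where the protocol groups them by treatment (probably a dropped phrase); separately, the emergent-value rule misses same-direction worsening

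*SAP*

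**What the plan says.** **Grouping.** In SAP 4.5 the statistical method cell for biochemistry, haematology and haemostasis has values, position against the laboratory range and clinical assessment "described at screening, baseline, each scheduled assessment during treatment phase and at end of study visit overall". SAP 4.6 ends its vital-sign sentence on values and range position in the same way: "each scheduled assessment during treatment phase and at end of study visit overall". SAP 4.8 repeats this for ECG. In all three cells, change from baseline is specified by dose group and overall, and emergent values are listed by dose group and subject.

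Protocol 10.1.2.3 describes laboratory values, range position and clinical assessment "during the treatment phase and at the end of study by treatment for studies and overall". For vital signs and ECG, Protocol 10.1.2.2 says that "values and clinically potentially significant abnormalities will be described by treatment and overall".

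Two further table titles name no grouping: "Vitals: Result and clinical significance at each day(time) point assessment from screening to end of study" and "ECG: Result and clinical significance at each day(time) point assessment from screening to end of study". By contrast, the qualitative urinalysis title in SAP 4.5 does: "Result at screening, baseline, during treatment phase and at end of study visit by dose group and overall".

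**Emergent values.** SAP 4.5, 4.6 and 4.8 count a value as emergent in two situations: a normal baseline becoming abnormal, or a "lower (upper) abnormal baseline value becoming upper (lower) abnormal at post-dose assessment". Protocol 4.1 lets subjects enter with out-of-range laboratory values judged clinically non-relevant, and makes a similar allowance for blood pressure, heart rate and ECG.

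**The concern.** Laboratory tests, vital signs and ECG are primary evaluation criteria in a placebo-controlled dose-escalation study. Their main descriptive use is comparison of each dose with placebo. A programmer who follows the method cells as written would produce tables of values and abnormality counts with every subject in one column, which cannot show whether abnormalities gather at one dose.

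The second issue is independent of the first. A listing of emergent values draws the reader to what changed after dosing. If a subject starts just outside the range and then moves far outside it, that listing stays silent, while a trivial crossing of the limit by another subject is shown.

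**Working it through.** **1. Grouping, side by side**

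| Summary | Protocol | SAP method cell | SAP table title |
|---|---|---|---|
| Laboratory values, range position, clinical assessment | by treatment and overall (10.1.2.3, clumsily worded) | overall (4.5) | no grouping named |
| Vital-sign and ECG values | by treatment and overall (10.1.2.2) | overall (4.6, 4.8) | no grouping named; values and change share one title |
| Vital-sign and ECG abnormalities | potentially significant abnormalities, by treatment and overall (10.1.2.2) | range position, overall (4.6, 4.8) | no grouping named |
| Change from baseline, all three | by treatment and overall | by dose group and overall | no grouping named |
| Qualitative urinalysis results | listed by treatment (10.1.2.3) | no grouping named | by dose group and overall |

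For the quantitative criteria, no title restores the grouping that the values sentence omits.

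**2. How many criteria are affected**

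- Blood (SAP 4.5): 24 biochemistry + 14 haematology + 4 haemostasis = 42.
- Urine pH and specific density, which SAP 4.5 sends to the same method: 2.
- Vital signs (SAP 4.6): 3 supine + 3 standing + temperature = 7.
- ECG (SAP 4.8): heart rate, PR, QRS, QT, QTcF = 5.
- Total: 42 + 2 + 7 + 5 = 56.

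Range position can be illustrated only where the documents give a range. The laboratory ranges appended to the SAP give a fixed range for 42 − 2 = 40 blood parameters: reticulocytes have none, and aPTT in seconds depends on the reagent lot. SAP Section 6 gives ranges for 4 vital signs (supine SBP, DBP and HR, and temperature) and 3 ECG intervals (PR, QRS, QTcF). Total: 40 + 4 + 3 = 47.

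**3. Effect of pooling in Part A**

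- Planned subjects (Protocol 1.6): 4 × (6 active + 2 placebo) = 24 + 8 = 32.
- Two abnormal subjects at one dose: 2/6 = 33.3% by dose; 2/32 = 6.25% overall.
- A mean shift confined to one active group would appear in the pooled mean at 6/32 = 18.75% of its size.

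**4. The emergent rule**

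With three states (low, normal, high) there are 3 × 3 = 9 baseline-to-post-dose transitions. The rule flags four: normal to low, normal to high, low to high, high to low. It never flags high to high or low to low, whatever the size of the change.

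Where a parameter has one limit, there is no opposite side to cross to, so an abnormal baseline can never become emergent. In the appended ranges these are AST, ALT, CPK, total bilirubin, conjugated bilirubin, triglycerides and LDL (upper limit only), and HDL and prothrombin level (lower limit only): 7 + 2 = 9, and 9/40 = 22.5%. QRS and QTcF behave the same way because their lower bound in SAP Section 6 is 0.

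Illustration with assumed values, for a man (appended ALT limit 42 U/L):

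- 40 to 45: change 45 − 40 = +5, emergent.
- 45 to 130: change 130 − 45 = +85, and 130/42 = 3.10 times the limit, not emergent.

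**The case against.** **On grouping.** The strongest reply is that this is editorial. The adjacent sentence in each cell carries the dose grouping, the vital-sign and ECG titles put values and change in one table, and the urinalysis title supplies a grouping that its own method cell lacks. Titles that name no grouping are common in this SAP, so silence in the result-and-clinical-significance titles does not prove that those tables are ungrouped. All of this stands, and makes a dropped phrase the likeliest explanation. It does not remove the need for correction, because the words as they stand specify something else.

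A reader might infer that dose-level safety information is lost, or that escalation would rest on pooled tables. The documents do not support either inference. Change from baseline and emergent listings are by dose group. SAP Section 5 lists individual data by dose group and subject, although its vital-signs list does not name standing blood pressure or heart rate. Treatment-emergent adverse events are summarised by dose group (SAP 4.4). Escalation uses a separate blinded review (Protocol 3.3.3.2).

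**On the emergent rule.** The ALT example would not go unseen. SAP 3.2 requires minimum and maximum, so the largest reported ALT change for that dose group and visit would be at least +85. A clinically significant value is an adverse event (Protocol 8.3.1), and the SAP's treatment-emergent definition counts worsening. At 130 U/L the value also exceeds 3 × 42 = 126, the individual ALT threshold in Protocol 3.5.2. These points stand as partial cover. They do not cover a moderate worsening judged not clinically significant that is not the extreme of its group.

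It is also fair that Part A has only two scheduled post-dose laboratory assessments (D2 and D4), so a worst-value table adds a limited amount.

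**Conclusion.** Both parts hold; the severity is minor to moderate.

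1. The SAP omits a treatment grouping that the protocol specifies: values, range position and clinical assessment for laboratory tests, and values and potentially significant abnormalities for vital signs and ECG. Read literally, the pooling touches 56 criteria, and the 2/6 versus 2/32 illustration can be shown for 47 of them. Some laboratory ranges may exist only in the database, so 47 is the number documented here. The loss is confined to the by-dose tables of values and abnormality frequency. SAP 3.1 says the plan takes account of the protocol's methods and announces no departure, so the documents do not support reading the omission as a deliberate change.

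2. The emergent rule leaves out same-direction worsening. It might be read as contradicting the protocol, but the protocol defines no emergent value, so this is a gap in an SAP listing. The documents give no frequency of out-of-range baselines, so how often it would matter is unknown.

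The denominators assume the planned 32 subjects in Part A. The abnormality counts and ALT values are illustrative assumptions.

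**What to change.** **Grouping.** In the method cells of SAP 4.5, 4.6 and 4.8, change the values sentence from *overall* to by dose group and overall. Put the same grouping in the matching table titles and in the vital-sign and ECG result-and-clinical-significance tables. State once, for all of SAP Section 4, that placebo is its own dose group, rather than editing each cell.

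**Emergent rule.** Keep the definition. For parameters with a reference range only, add a shift table by dose group from baseline to the worst scheduled post-dose value, with lowest and highest shown separately where there are two limits. Include a category for subjects out of range at baseline who move further out in the same direction, and show the size of the change. Apply the repeat-assessment rule of SAP Section 3, leaving repeats in the listings.

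**Cost.** A few words in the SAP, and programming on data already collected for one extra table. The downside is that small drifts beyond an already exceeded limit will appear and, with 6 active subjects per dose, many cells will be sparse. Showing the size of change lets the reader discount trivial drifts, and nothing extra is flagged as emergent.
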